With regard to follow-up, at 6 months, participants will be mailed a very brief follow-up questionnaire and at each anniversary date a more detailed questionnaire and a re-supply of calendar packs. The questionnaire will include items on compliance with randomized treatments, use of non-trial supplements of vitamin D and fish oil, use of calcium supplements, development of major illnesses, dietary intakes of vitamin D and fish, and updated risk factors related to cancer and CVD. Information on potential side effects of the study agents will be elicited for monitoring by the Data and Safety Monitoring Board. For fish oil, these side effects include GI symptoms (burping, stomach upset or pain, nausea, constipation, diarrhea), bleeding (any GI bleed, GI bleeding, hematuria, easy bruising, epistaxis), skin rash, colds or upper respiratory tract infection, flu-like symptoms, and bad taste in mouth. For vitamin D, these side effects include GI symptoms, and physician diagnosis of hypercalcemia or kidney stones, both of which are not expected to occur at the dose used in VITAL.² Non-responders will be mailed a second and third request and will then be telephoned to collect study data. If phone contact fails, a fourth request will be mailed in order to ascertain the participant's study status and to obtain minimum information regarding the primary study outcomes. Participants will also be given the option of completing an electronic questionnaire sent via e-mail. These data will be collected and managed using REDCap electronic data capture tools. REDCap (Research Electronic Data Capture) is a secure, HIPAA-compliant web-based application hosted by PartnersHealthCare Research Computing.

Internet sources will be used to assist in the tracking (new address, new phone number) of participants who are potentially lost to follow-up. At the very least, vital status will be ascertained. Participants will be instructed to discontinue their study capsules if, during follow-up, they receive a diagnosis of hypercalcemia, sarcoidosis, or other safety-exclusion conditions and to inform their physicians about their participation in VITAL. If, in the course of follow-up,

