Participants who self-report one of the above study endpoints will be asked to sign a medical release form authorizing VITAL staff to obtain hospital/physician records. The request will be accompanied by a cover letter expressing sympathy for the diagnosis and explaining HIPAA guidelines and the scientific importance of record validation. Non-responders will be sent two additional requests for the medical release form. After the release is obtained, a copy will be sent to the treating hospital/physician. If there is no response within 1 month, a second request will be mailed, followed by a phone call.

Beginning in the fall 2016, to increase the completeness of outcome information regarding MI, stroke, revascularization procedures of CABG and PCI, and cancer, information will be requested from Medicare (the Centers for Medicare and Medicaid Services). To obtain the information, participants will be identified using date of birth and social security number (if previously provided by the participant). The information will include medical diagnoses from hospitalizations, emergency room visits, as well as the names of procedures funded by Medicare. The information does not include test result or actual medical records. To obtain this

specific information, participants will be contacted directly in order to gain their written permission for the release of this information (see above.)

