Beyond the primary analyses, we will conduct prespecified secondary analyses to examine effect modification by the other randomized intervention, by baseline risk factors, by compliance, and by time. We have a particular interest in exploring interactions between the interventions, as well as with the baseline plasma biomarkers of 25(OH)D for vitamin D and of EPA+DHA for fish oil. We hypothesize that the intervention effects may be larger among those with below-median baseline levels, and will examine treatment effects by quartiles of these biomarkers. The biomarker data will be analyzed as a case-cohort study using methods for proportional hazards regression.⁷⁷ Because of the frequency matching by age and gender, appropriate stratum-specific weighting of the observations will be employed.⁷⁸ We also have a prior interest in the effects of the vitamin D intervention within groups defined by race/ethnicity and skin pigmentation, and by BMI. In addition, we will evaluate effect modification by age and gender, as well as by sunlight exposure, calcium and phosphorus intakes from the FFQ (as these nutrients affect vitamin D bioavailability⁷⁹), and baseline risk factors for cancer and CVD. The latter interaction effects will be interpreted cautiously, as hypothesis generating. We will also examine as a prespecified secondary analysis the association among compliers, in which participants' follow-up time will be censored when they are no longer compliant with taking at least two-thirds of their assigned active agents or placebos. Finally, we will examine whether treatment effects vary over time and duration of treatment by examining survival plots and interactions with time. We will additionally conduct analyses for the primary endpoints of cancer and cardiovascular disease excluding events occurring in Year 1, as well as in Years 1 and 2, of follow-up. There may be a latent effect on both outcomes, depending on the mechanisms by which these agents act.

We will also compare the incidence of potential side effects in the active v. placebo groups for each agent, including the incidence of kidney stones with vitamin D assignment (cf. WHI calcium-vitamin D findings⁴⁴) and the incidence of GI symptoms, skin abnormalities, and bleeding with fish oil assignment (cf. JELIS findings⁴¹).

B. POWER CALCULATIONS

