Potential side effects of the study agents will be assessed on each follow-up questionnaire. For fish oil, these side effects include gastrointestinal (GI) symptoms (burping, stomach upset or pain, nausea, constipation, diarrhea), bleeding (any GI bleed, GI bleeding requiring transfusion, hematuria, easy bruising, epistaxis), skin rash, colds or upper respiratory tract infection, flu-like symptoms, and bad taste in mouth. A recent study reported that men with high blood levels of omega-3 fatty acids, which are found in fish and fish oil supplements, were more likely to develop prostate cancer than men with low blood levels of omega-3 fatty acids.⁸¹ However, because this was an observational study and not a randomized trial, the findings could be spurious, resulting from confounding bias. The VITAL trial will be collecting information on new diagnoses of prostate cancer, assessed on each follow-up questionnaire by self-report and confirmed on medical record review. For vitamin D, side effects include GI symptoms; and physician diagnosis of hypercalcemia or kidney stones, both of which are not expected to occur at the dose used in VITAL.²

There is also the possibility of social/psychological risk that could result from inadvertent disclosure of confidential information from the questionnaires or blood tests. However, we have many safeguards in place to avoid this possibility, and we have never had an inadvertent breach of confidentiality in any of our trials.

With regard to the risks of the study agents, information on potential side effects discussed above will be elicited on each follow-up questionnaire for monitoring by the Data and Safety Monitoring Board. We will compare the incidence of potential side effects in the active v. placebo groups for each agent, including the incidence of kidney stones with vitamin D assignment and the incidence of GI symptoms, skin abnormalities, and bleeding with fish oil assignment.

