Similar analyses will be conducted for both cancer and CVD. For cancer, we will estimate the intervention effects on the primary endpoint of total cancer, as well as the secondary outcomes of breast, prostate, and colorectal cancer, and cancer mortality. For CVD we will estimate the effects on the primary composite endpoint of major CVD (MI, stroke, and cardiovascular mortality); on the secondary composite endpoint that additionally includes coronary revascularization; and on the individual components of MI, stroke, revascularization, and cardiovascular mortality.

Beyond the primary analyses, we will conduct prespecified secondary analyses to examine effect modification by the other randomized intervention, by baseline risk factors, by compliance, and by time. We have a particular interest in exploring interactions between the interventions, as well as with the baseline plasma biomarkers of 25(OH)D for vitamin D and of EPA+DHA for fish oil. We hypothesize that the intervention effects may be larger among those with below-median baseline levels, and will examine treatment effects by quartiles of these biomarkers. The biomarker data will be analyzed as a case-cohort study using methods for proportional hazards regression.⁷⁷ Because of the frequency matching by age and gender, appropriate stratum-specific weighting of the observations will be employed.⁷⁸ We also have a prior interest in the effects of the vitamin D intervention within groups defined by race/ethnicity and skin

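### The planned fish oil bleeding comparison has no intracranial bleeding, and stroke is analysed only as an untyped efficacy endpoint

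*Combined protocol and SAP*

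**What the plan says.** All references are to the final protocol unless stated.

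- **Bleeding items.** Follow-up (V.D) lists "bleeding (any GI bleed, GI bleeding, hematuria, easy bruising, epistaxis". Treatment (V.C) and Risks and Discomforts (VII) give "bleeding (any GI bleed, GI bleeding requiring transfusion, hematuria, easy bruising, epistaxis". None of the three lists names intracranial bleeding.
- **Source and comparison.** Section VII states: "Potential side effects of the study agents will be assessed on each follow-up questionnaire". Sections VI.A and VII, and VI.A of the final SAP, then plan a comparison by arm of "the incidence of GI symptoms, skin abnormalities, and bleeding with fish oil assignment". They give no definition, severity tier or confirmation rule for bleeding.
- **Record confirmation.** In V.E, "Participants who self-report one of the above study endpoints will be asked to sign a medical release form". Bleeding is not among the endpoints listed there.
- **Stroke.** Stroke is part of the primary CVD composite, and VI.A of the protocol and SAP also plans to estimate effects "on the individual components of MI, stroke, revascularization, and cardiovascular mortality". No stroke type is named. V.E categorizes strokes by the TOAST criteria, and the reference given for these (72) is titled as a classification of acute ischemic stroke subtypes.
- **Deaths.** The Endpoints Committee reviews the records and assigns an ICD code (V.E).
- **Medicare.** V.E adds a linkage that starts in fall 2016 and gives its purpose as follows: "to increase the completeness of outcome information regarding MI, stroke, revascularization procedures of CABG and PCI, and cancer, information will be requested from Medicare". Hospital and emergency room diagnoses are in the file. Linkage uses the social security number, which was optional at enrollment.
- **DSMB.** It reviews unblinded endpoints and possible adverse effects every year (IX.A).

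**The concern.** Bleeding is a named fish oil risk with its own planned comparison, and IX.A says the trial is meant to weigh benefits against risks. The bleed with the gravest consequences is missing from that comparison. If hemorrhagic strokes are confirmed at all, they enter under stroke, where they are pooled with the ischemic events that the agent is hoped to prevent. Effects in opposite directions would partly cancel there. The result could read as little or no effect on stroke, with nothing in the bleeding comparison to show that two effects lay beneath it. The records needed to separate them are already to be collected and reviewed blind.

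**Working it through.** **1. The text.** The plan gives no rate or power for bleeding or hemorrhagic stroke, so there is no stated figure on the point itself to reproduce. Its sections set side by side:

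| Event | Source | Confirmed? | In the bleeding comparison? |
|---|---|---|---|
| GI bleed, hematuria, bruising, epistaxis | questionnaire | no | yes |
| GI bleed needing transfusion | questionnaire (V.C, VII; qualifier absent in V.D) | no | yes, if V.C and VII govern |
| Hemorrhagic stroke | presumably under stroke; never named | as a stroke | no |
| Fatal bleed | ICD-coded cause of death | yes | not stated |

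**2. How many strokes the power table implies.** Final protocol VI.B, CVD power table, stroke column: 60.3, 80.3, 92.8, 98.2 and 99.7% at RR 0.80, 0.75, 0.70, 0.65 and 0.60 (two-sided 0.05, 25,000 participants). Freedman's formula is D = (1.96 + z_power)² × ((1+RR)/(1−RR))².

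- RR 0.80: (1.96 + 0.261)² × 81 ≈ 400
- RR 0.75: (1.96 + 0.852)² × 49 ≈ 388
- RR 0.70: (1.96 + 1.461)² × 32.1 ≈ 376

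These are totals under each assumed benefit. With no effect, the middle row gives 388 × 2/1.75 ≈ 443. Calibrated on that one row, Freedman returns 60.2, 92.8, 98.2 and 99.7% for the others, so the column is internally consistent. The same calibration with Schoenfeld's formula gives about 437.

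**3. Offsetting.** Assumption, not in the documents: a share h of 10-20% of strokes is hemorrhagic. That is about 40-80 of the 376-400 strokes. The component RRs below are also illustrative. Pooled RR = h × RR_hem + (1−h) × RR_isch.

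- RR_hem 1.5, RR_isch 0.90: 0.15 + 0.81 = 0.96 at h = 0.10; 0.30 + 0.72 = 1.02 at h = 0.20
- RR_hem 2.0, RR_isch 0.90: 0.20 + 0.81 = 1.01; 0.40 + 0.72 = 1.12
- RR_hem 1.5, RR_isch 0.75: 0.15 + 0.675 = 0.825; 0.30 + 0.60 = 0.90

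In the last case, the 80.3% power stated for a stroke RR of 0.75 falls to about 48% and 19% at the pooled RRs (Schoenfeld, 437 events under no effect).

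**4. What a separate comparison could show.** Schoenfeld: power = Φ(½√D × ln RR − 1.96).

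| D | RR 2.0 | RR 1.5 |
|---|---|---|
| 40 | Φ(3.16 × 0.693 − 1.96) ≈ 59% | Φ(3.16 × 0.405 − 1.96) ≈ 25% |
| 80 | Φ(4.47 × 0.693 − 1.96) ≈ 87% | Φ(4.47 × 0.405 − 1.96) ≈ 44% |

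A more favourable count takes the no-effect total (10-20% of 437, or 44-87) and lets the active arm's half grow, so that D = (H/2)(1+RR). Power is then about 80-98% for a doubling and 32-56% for a 50% increase.

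**The case against.** The bleeding comparison is not confined to minor symptoms. V.C and VII keep transfused GI bleeds, and VII sends the effects it lists to the DSMB and to the by-arm comparison. A reader might infer from V.D that the severity marker has been lost. The text does not support that: V.D names GI bleeding twice in a way that looks like a dropped phrase, and the sections need only be reconciled.

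Nor do strokes escape safety oversight. The DSMB sees unblinded endpoints beside adverse effects and may weigh secondary endpoints. This stands, but no split by stroke type is specified for its review or for the final analysis.

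That hemorrhagic strokes are counted is inferred from the unqualified word stroke. This too is fair, and it means the typing rule must be stated before any comparison can be made.

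Non-response is a weak ground. The restricted mailing, "a fourth request will be mailed in order to ascertain the participant's study status and to obtain minimum information regarding the primary study outcomes", follows three requests and a telephone attempt to collect study data, and nothing in the documents suggests that the remaining loss would differ by arm.

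The prior for harm may be low. V.C cites a view that the side-effect risks are low or very low up to 1 g/d, and anticoagulant users are excluded at baseline. A separate comparison would more likely than not miss a 50% increase at 40-80 events. Both points limit what the comparison can show. Neither is a reason to leave the most serious bleed out of it.

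**Conclusion.** The point holds in a bounded form. As written, the fish oil bleeding comparison is unconfirmed self-report without intracranial bleeding, and no stroke-type analysis is planned, so an adverse effect on hemorrhagic stroke could be offset in the stroke endpoint. The pooled RR of 0.96-1.02 depends on the assumed 10-20% hemorrhagic share and on illustrative RRs of 1.5 and 0.90. It shows that masking is possible, not that it is expected.

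Two wider readings should be avoided. A reader might infer that the vitamin D harms are also ascertained only by questionnaire. For hypercalcemia this is wrong, because V.A examines blood calcium and PTH as markers of it. A reader might also infer that the Medicare file would capture the missing serious bleeds. It starts in fall 2016, the intervention ended on December 31, 2017, and linkage needs an optional identifier, so it could only supplement.

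**What to change.** 1. In V.E, have the Endpoints Committee record each confirmed stroke as ischemic, hemorrhagic or unknown, and keep TOAST for ischemic subtypes.
2. In VI.A of the protocol and SAP, and in the reports to the DSMB, compare hemorrhagic stroke and fatal bleeds (from the ICD-coded cause of death) by fish oil assignment as bleeding safety outcomes. Show ischemic stroke beside them, with confidence intervals and a statement that a null result does not exclude harm.
3. Reconcile the bleeding list in V.D with those in V.C and VII.
4. Optionally, report bleeding diagnoses in the Medicare file as supportive, unvalidated data, limited to participants who gave a social security number.

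The cost is one field on the stroke review and a few table rows drawn from records already under blinded review. The Medicare step would also need the stated purpose of that request widened. The primary analysis is unchanged.

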2. To explore whether the effect of vitamin D₃ or EPA+DHA supplementation on cancer and CVD risk varies by (a) baseline blood levels of these nutrients, (b) race/skin pigmentation (for vitamin D₃), and (c) body mass index (BMI) (for vitamin D₃).
3. To explore whether vitamin D₃ and EPA+DHA supplementation reduces the risks of heart failure.

III. SUBJECT SELECTION

Study population: VITAL will be conducted among 26,500 apparently healthy participants. Included in the trial will be men aged ≥ 50 and women aged ≥ 55 , ages at which rates of chronic disease increase substantially. Excluded from the study will be individuals who have (1) a history of cancer (except non-melanoma skin cancer), MI, stroke, TIA, CABG, or PCI; (2) have any of the following safety exclusions: use of anticoagulants at baseline, history of renal failure or dialysis, hypercalcemia, hypo- or hyperparathyroidism, severe liver disease (cirrhosis), or sarcoidosis or other granulomatous diseases such as active chronic tuberculosis or Wegener's granulomatosis; (3) have an allergy to fish (for EPA+DHA); (4) have another serious illness that would preclude participation; (5) are consuming greater than 800 IU of vitamin D from all supplemental sources combined (individual vitamin D supplements, vitamin D analogues, calcium+vitamin D supplements, medications with vitamin D [e.g., Fosamax Plus D], and multivitamins), and are not willing to decrease or forego such use during the trial (to ensure total supplemental vitamin D intake does not exceed the current safety limit [i.e., tolerable upper intake level of 4000 IU/d set by the Institute of Medicine²); (6) are consuming greater than 1200 mg/d of calcium (the RDA for men aged >70 years and women aged >50 years²) from all supplemental sources combined; (7) are taking fish oil supplements and are not willing to forego their use during the trial; and (8) are not willing to participate, as evidenced by not signing the informed consent form. Although thiazide diuretics and supplemental vitamin D may interact to increase hypercalcemia risk, it is unlikely that such an interaction would occur at the vitamin D dose we propose.⁴⁵ Thus, thiazide use will not be an exclusion criterion.

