Run-in: The experience of other studies conducted by our research group (PHS, WHS, and WAFACS) has demonstrated the success of a run-in period in identifying a group of excellent compliers for long-term follow-up. Because the health experience of participants will be analyzed according to randomized treatment assignment, the use of a run-in phase to eliminate poor compliers prior to randomization will increase the power of the study.⁴⁶ During a 3-month run-in period, all participants will take placebo vitamin D softgel capsules and placebo fish oil. As the effects of both agents on cancer prevention are likely to be chronic, it would not be scientifically appropriate to use active agent in the run-in and then randomize to placebo. Moreover, the use of placebos will allow us to most clearly analyze the side effects of the study agents during the randomized treatment period.

At trial enrollment, willing and eligible participants will be mailed a 6-month supply of run-in calendar packs (i.e., 3 months for the actual run-in and 3 months to allow pill-taking to continue uninterrupted while we check participants' responses for continued eligibility and then ship randomized capsules to participants who remain eligible). Participants will take two capsules per day (one vitamin D placebo softgel capsule and one fish oil placebo capsule). At 3 months, participants will receive a follow-up run-in questionnaire asking about continued eligibility,

willingness to continue in the trial, pill compliance, and potential side effects. Non-responders will be mailed up to 3 requests at 6-week intervals.

Participants will be randomized only if they: (1) demonstrate good compliance in pill taking, defined as taking at least two-thirds of the study pills during the run-in (i.e., missed 10 or fewer days of pill taking in the past month); (2) express willingness to continue in the trial; (3) report no new history of cancer (except non-melanoma skin cancer), MI, stroke, TIA, CABG, PCI, hypercalcemia, sarcoidosis, kidney failure or dialysis, parathyroid disease, cirrhosis or other severe liver disease, or other serious illness, use of anticoagulants or vitamin D analogues, during the run-in; (4) are consuming no more than 1200 mg/d of calcium (the RDA for men aged >70 years and women aged >50 years²) from all supplemental sources combined; and (5) demonstrate continued willingness to limit supplemental vitamin D intake to ≤ 800 IU/d and to forego the use of fish oil supplements.

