A modified version of a validated, self-administered semi-quantitative food frequency questionnaire (FFQ) will be mailed to participants during the run-in. The original questionnaire, developed by [name], DrPH, and colleagues, is an efficient, reliable, and accurate instrument for categorizing individuals according to their intake of 32 nutrients, including vitamin D and marine omega-3 fats.⁴⁸⁻⁵³ Participants will be asked to estimate their average intake over the past year of various foods, beverages, and supplements that contain vitamin D, marine omega-3 fats, and other nutrients. Dietary vitamin D intake will be estimated from participants' reported intakes of certain foods, including dairy products, fortified breakfast cereals, fortified juices, dark-meat fish, and cod liver oil. Dietary marine omega-3 fat intake will be estimated from intake of dark-meat fish, canned tuna, other fish, and seafood. Classifying participants by baseline intake of various nutrients will allow us to evaluate whether the study agents' effects vary by such intake. Participants will also be asked to complete the FFQ at 4+ years, enabling an examination of dietary changes over time.

Questions on use of non-study supplements or drugs containing vitamin D or EPA+DHA will be asked at baseline, 6 months, and on yearly follow-up questionnaires. We will also assess flaxseed and alpha-linolenic acid intakes. We will ascertain and analyze intake from food and supplements separately, and from both sources combined.

C. TREATMENT

In our research application, we proposed testing 1600 IU (40 µg) per day of vitamin D₃ (cholecalciferol) in VITAL. Since the application was submitted, based on new research and with approval from NCI, we now will test 2000 IU (50 µg) per day instead. We seek to obtain a large-enough difference in vitamin D status between the treatment and placebo groups to detect health benefits, and there appear to be few safety issues associated with this dose. Recent studies have found little toxicity risk with doses up to 10,000 IU/d.⁴⁵ (Nevertheless, to further

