participants report taking supplementary vitamin D (not from diet) that amounts to greater than 800 IU per day or daily calcium supplements that amount to greater than 1200 mg per day, they will be asked to limit their intakes to study guideline levels. These instructions will be included in the study guidelines which accompany each shipment of calendar packs.

At 6-month intervals between annual follow-ups, participants will be mailed an interim form with questions on the development of primary endpoints (cancer, MI, and stroke), difficulties with pill compliance, and address changes. Participants will be asked to return the form only if one or more questions apply. The interim follow-up will help the staff maintain accurate contact information and provide a head start in addressing compliance issues and timely collection of medical records to confirm endpoints.

A newsletter will be mailed to participants twice each year. The newsletter will keep participants up-to-date regarding the progress of the study and also touch upon health topics that are related to the study such as prevention of cardiovascular disease and cancer or current research findings.

At the end of pill-taking, for the following two years, an annual questionnaire will be mailed to participants. The form will be similar to the conventional follow-up questionnaires, collecting information about potential risk factors for cancer and cardiovascular disease, use of medications, and medical history. The additional data will be used to address the main research questions and to examine new hypotheses regarding health promotion and disease prevention.

E. ENDPOINT ASCERTAINMENT AND VALIDATION

The primary cancer endpoint of VITAL will be total cancer incidence (excluding non-melanoma skin cancer), with cancer mortality and the individual sites of colorectal, breast, and prostate cancer as secondary endpoints. For CVD, the primary endpoint will be a composite endpoint of MI, stroke, and CVD mortality. Secondary endpoints will include a second composite endpoint adding revascularization procedures of CABG and PCI, as well as the individual endpoints of MI, stroke, revascularization, and CVD mortality. Additional endpoints of interest include heart failure, colorectal polyps, and periodontal disease.

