pigmentation, and by BMI. In addition, we will evaluate effect modification by age and gender, as well as by sunlight exposure, calcium and phosphorus intakes from the FFQ (as these nutrients affect vitamin D bioavailability⁷⁹), and baseline risk factors for cancer and CVD. The latter interaction effects will be interpreted cautiously, as hypothesis generating. We will also examine as a prespecified secondary analysis the association among compliers, in which participants' follow-up time will be censored when they are no longer compliant with taking at least two-thirds of their assigned active agents or placebos. Finally, we will examine whether treatment effects vary over time and duration of treatment by examining survival plots and interactions with time. We will additionally conduct analyses for the primary endpoints of cancer and cardiovascular disease excluding events occurring in Year 1, as well as in Years 1 and 2, of follow-up. There may be a latent effect on both outcomes, depending on the mechanisms by which these agents act.

We will also compare the incidence of potential side effects in the active v. placebo groups for each agent, including the incidence of kidney stones with vitamin D assignment (cf. WHI calcium-vitamin D findings⁴⁴) and the incidence of GI symptoms, skin abnormalities, and bleeding with fish oil assignment (cf. JELIS findings⁴¹).

B. POWER CALCULATIONS

To calculate power, the following assumptions were made: (1) a 2x2 factorial trial in 12,500 men aged ≥ 50 and 12,500 women aged ≥ 55 ; (2) independent and equal allocation of participants to each treatment; (3) an age distribution based on that observed at baseline in our past trials for men aged ≥ 50 and women aged ≥ 55 ; (4) age-specific event rates based on the observed rates in the first 5 years of the PHS II for men and the WHS for women; (5) trial follow-up of 5 years, with little loss to follow-up as achieved in our past trials; and (6) compliance similar to that in published trials upon which our estimated rate ratio (RR) reductions are based. The cited reductions are thus the observed effects we would see in the trial. The corresponding 'true' RR is given assuming an average compliance of 80%. Power is given for a two-sided test using a logrank analysis⁸⁰ with a significance level of 0.05.

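### The compliers analysis treats placebo participants who take outside fish oil as compliant, and the protocol states no follow-up step for such use although forgoing it is a condition of randomization

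*Combined protocol and SAP*

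**What the plan says.** Entry (final protocol, III, exclusion 7): people are excluded if they "are taking fish oil supplements and are not willing to forego their use during the trial". The screening criteria in section IV repeat this. The run-in criteria (IV, item 5) require continued willingness "to forego the use of fish oil supplements" before randomization.

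Measurement: under V.B, questions on non-study products containing vitamin D or EPA+DHA "will be asked at baseline, 6 months, and on yearly follow-up questionnaires". V.D lists "use of non-trial supplements of vitamin D and fish oil" among the follow-up items. V.A plans follow-up blood samples at years 2 and 4 in a subset of 6000, with EPA+DHA assayed.

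Follow-up step: V.D acts when "participants report taking supplementary vitamin D (not from diet) that amounts to greater than 800 IU per day or daily calcium supplements" above 1200 mg per day are reported. In that case "they will be asked to limit their intakes to study guideline levels", and these instructions go out with each shipment of calendar packs. Fish oil is not named.

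Analysis: the compliers analysis (VI.A of the final protocol and of the final SAP) censors participants "when they are no longer compliant with taking at least two-thirds of their assigned active agents or placebos". Outside use plays no part in that definition.

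**The concern.** The entry condition on fish oil protects the contrast between the active and placebo arms. After randomization, the protocol collects the information needed to see whether the condition is kept, but states neither a step nor a treatment-effect analysis that uses it.

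The consequence is clearest in the compliers analysis. Its purpose is to compare people who took the agent with people who did not. A placebo participant who takes the placebo capsules and a retail fish oil product is exposed to the agent, yet contributes unexposed, compliant person-time. If fish oil has an effect, the estimate moves toward the null in the analysis meant to reduce dilution. The same gap exists for a vitamin D placebo participant who reports more than the permitted 800 IU/d.

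The power section discounts for 80% compliance and states no separate allowance for outside use in the placebo arm.

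**Working it through.** **One participant followed through the text.** Take someone assigned to fish oil placebo who takes more than two-thirds of the capsules and reports daily retail fish oil at year 1. The run-in criterion was met at randomization. The step in V.D is not triggered, because neither the vitamin D nor the calcium limit is exceeded. Under VI.A the person remains compliant for as long as the capsules are taken.

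**Inputs from VI.B (final protocol).** 12,500 men and 12,500 women, equal allocation, two-sided logrank test at 0.05, 80% compliance. Stated power for major CVD is 41.6%, 75.6%, 94.8% and 99.5% at observed RR 0.90, 0.85, 0.80 and 0.75.

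**Assumption.** A share d of the placebo arm takes outside fish oil throughout, with the full effect of the study capsule. The documents give no value for d; 0 to 30% is shown.

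**Step 1: the plan's dilution.** Observed RR = 1 − 0.80 × (1 − true RR). This turns 0.875 into 0.90, 0.75 into 0.80 and 0.50 into 0.60, as tabulated. No placebo-arm term is needed to reproduce the tables.

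**Step 2: the plan's power.** Power = Φ(√E × (1 − RR)/(1 + RR) − 1.96), with E = E0 × (1 + RR)/2 and E0 the events expected with no effect. No event count is tied to this table (the 990 CVD cases in V.A are the same figure as in the original 20,000-person protocol), so E0 was solved from the table. E0 = 1159 returns 41.6%, 75.6%, 94.8% and 99.5%. For total cancer, E0 = 1916, solved from 92.7% at RR 0.85, returns the 0.90 and 0.80 rows within 0.2 points. These are consistency checks, since E0 comes from the same tables.

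**Step 3: add outside use.** Observed RR = (1 − 0.80(1 − R))/(1 − d(1 − R)), and E = E0 × (numerator + denominator)/2. For major CVD with true RR 0.75 and d = 10%: RR = 0.80/0.975 = 0.821; E = 1159 × (0.80 + 0.975)/2 = 1029; power = Φ(3.16 − 1.96) = 88.5%.

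| d | Major CVD, true RR 0.75: observed RR | Power | Total cancer, true RR 0.8125: observed RR | Power |
|---|---|---|---|---|
| 0% | 0.800 | 94.8% | 0.850 | 92.7% |
| 5% | 0.810 | 92.2% | 0.858 | 89.4% |
| 10% | 0.821 | 88.5% | 0.866 | 85.1% |
| 15% | 0.831 | 83.8% | 0.875 | 79.8% |
| 20% | 0.842 | 77.9% | 0.883 | 73.5% |
| 30% | 0.865 | 63.0% | 0.901 | 58.2% |

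**Step 4: compliers analysis.** With capsule compliance complete by definition, estimated RR = R/(1 − d(1 − R)). At R = 0.75 this is 0.75/0.975 = 0.769 for d = 10% and 0.75/0.95 = 0.789 for d = 20%.

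**The case against.** The vitamin D and calcium step is a safety measure. Section III ties the 800 IU limit to a tolerable upper intake level, and V.C ties the calcium limit to hypercalcemia and kidney stones. The protocol regards omega-3 at these doses as low risk. A reader might infer that the sponsor applied one policy inconsistently across agents. The documents do not support that: the vitamin D rule was not written to protect the contrast, since placebo participants may take up to 800 IU/d. This point stands. The gap is an omission, not a contradiction between two equivalent rules.

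A reader might also infer that placebo participants who report fish oil are never reminded of their agreement. That cannot be known, because the guidelines mailed with each shipment are not in the documents. The protocol can only be said to state no step.

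Nor is the exposure unmonitored. It is asked about repeatedly and partly checked in blood, and V.B says intake from food and supplements will be analyzed. What is missing is any link from these data to the treatment-effect analyses.

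On size, the rate of outside use is assumed, and full effectiveness throughout follow-up is a severe assumption for people who agreed to abstain. VI.B bases compliance on published trials and tabulates power against the observed RR. If those figures already reflect control-arm use, the power loss above is double counted. The Background's dilution warning is mainly about food fortification, which this point does not address.

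Finally, censoring at reported outside use may be informative, because people may start fish oil when their perceived risk changes. That is a real cost, but in an analysis that already censors after randomization.

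**Conclusion.** The point holds for the exposure definition in the compliers analysis. As written, that analysis keeps placebo participants who use outside fish oil in the unexposed group, which biases a real effect toward the null. The bias is modest: a true 0.75 becomes 0.77 to 0.79 if 10% to 20% of placebo compliers use a fully effective product, and less if use is rarer, shorter or weaker.

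The effect on the intent-to-treat analysis is conditional. At the same rates in the placebo arm, power for major CVD would be 88.5% to 77.9% instead of 94.8%, but only if the 80% compliance figure does not already cover such use, on which the documents are silent. A reader might conclude that the primary analysis is invalid or the stated power wrong; neither follows. Outside use dilutes the contrast without inflating type I error, and the stated power reproduces under the plan's own assumptions.

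Separately, the fish oil entry condition has no stated counterpart in the follow-up text, and the two should be reconciled.

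**What to change.** 1. In VI.A of the final protocol and SAP, add to the compliers analysis, at least as a sensitivity version, that compliant time also ends at first reported regular non-study fish oil use for the fish oil comparison, and at reported supplemental vitamin D above the existing 800 IU/d limit for the vitamin D comparison. Apply the rule alike in active and placebo arms. Define regular use in terms of the questionnaire items before unblinding; the change summary dates investigator unblinding to 6 December 2017, so a rule written later should be labelled post hoc. State that this censoring may be informative and leaves fewer events. Active-arm users of outside fish oil, who remain exposed, are also censored.

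2. Reconcile the fish oil condition in sections III and IV with the follow-up text in V.D, so that the protocol says how reported use relates to the entry agreement. No clinical rule is proposed here. This part has limited practical value at the final version, since the intervention ended on 31 December 2017.

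The cost is a short addition to the SAP and a clarification in the protocol. The data are already collected, and the primary intent-to-treat analysis is unchanged.
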